7.3.1 Additional Analyses of Secondary Outcome

The primary analysis of the secondary outcome explicitly adopts a multiple imputation approach. Two sensitivity analyses will be conducted in which missing values are replaced with the lowest (highest) observed value in the assigned treatment arm.

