**Table 3. PATIENT STUDY CALENDAR:**

	Visit 1 (Screening)	Visit 2 (6 weeks +/- 1 week from last visit)	Visit 3 (6 weeks +/- 1 week from last visit)	Visit 4 (6 weeks +/- 1 week from last visit)	Visit 5 (3 months +/- 1 week from last visit)
Informed Consent	X				
Eligibility	X				
Medical History	X				
Vitals (VAS, HR, BP, RR, O2 Sat, Weight, Height)	X	X	X	X	X
Randomization		X			
Physical Exam	X	X	X	X	X
Pregnancy Test	X 				
Injection of pAF (1ml/5cm  )- Treatment group		X	X		
Burn Center SOC	X	X	X	X	X
Manual Measurement	X	X	X	X	X
Pain Assessment	X	X	X	X	X
Laboratory Tests	X			X	
Wound Culture Swabs	X	X	X	X	X
Digital Image	X	X	X	X	X
Adverse Events Noted		X	X	X	X
Wound assessment	X	X	X	X	X

Follow-up phone call to assess adverse events		X 	X 		
---	--	----------------	----------------	--	--

Only applicable to women of childbearing potential

Follow-up phone call within 24 hours AND 5-7 days after visit to assess adverse events and medications.

Applicable study procedures may be completed via telehealth or by phone, at the discretion of the treating provider.

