#### **DISCONTINUATION OF STUDY DRUG:**

pAF-specific treatment will be discontinued if any of the following occur:

- Discovery of new information which makes the subject ineligible to continue participation in the study. This could include systemic sepsis, disseminated infections requiring inpatient hospitalization, worsening infection of the wound, such as necrosis or surgical intervention, increase in wound size by 50% from Visit 2 measurement, development of osteomyelitis, etc.
- Severe allergic reaction possibly related to the investigational product.
- Patient receives any investigational agent/intervention to the wound outside the study visits or is non-compliant with care between Visits 2 and 3.
- Any other condition that in the opinion of the treating physician are not compatible with participation in this study.

The study PI, treating clinicians and research staff will monitor closely for the above events, as well as any additional adverse events that occur while the subject is receiving treatment. Adverse events will be reported immediately upon discovery of the event to the Data Coordinating Center and assessed for seriousness, relatedness, severity, and expectedness.

The DSMB will meet regularly to review adverse events, safety analyses and study data and will have access to the actual treatment assignments for each group.

If study drug is discontinued, we will continue to follow the patient and monitor for safety and efficacy endpoints.

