The primary analysis of the primary outcome implicitly adopts a last-observation-carried-forward approach. Multiple imputation will be used for the primary analysis of the secondary outcome and may also be used for other outcomes, as described in the Statistical Analysis Plan. Because the sample size is modest, it may not be feasible to use complex multiple imputation models, but candidate variables for the imputation of missing values for the secondary outcome will include variables such as assigned treatment arm and wound area measurements from other study visits. As sensitivity analyses, the analyses of the primary and secondary outcomes will be repeated twice, first replacing each missing outcome with the lowest observed outcome at that timepoint from among subjects in the same assigned treatment arm, and then again replacing each missing outcome with the highest observed outcome at that timepoint from among subjects in the same assigned arm.

A number of additional prespecified exploratory analyses will be conducted. Although the overall sample size is modest, subgroup analyses were requested by the FDA and will be conducted for the primary and secondary outcomes using subgroups defined by the following variables: sex; race; ethnicity; diagnosis of diabetes mellitus or a screening hemoglobin A1C greater than or equal to 6.5; use of immunosuppressive medications; presence/absence of known malignancy other than non-metastatic basal or squamous cell carcinoma; nutritional status as defined by albumin levels; presence/absence of blood coagulation conditions defined by PT/INR and PTT levels; presence/absence of venous vascular disease affecting the wound area; presence/absence of arterial vascular disease affecting the wound area; Visit

1 oxygen saturation  $<90\%$  or  $\geq 90\%$ ; and concomitant anticoagulation medication or lack thereof. The details of the subgroup analysis will be available in the Statistical Analysis Plan (SAP).

Finally, although some additional collected data elements may influence the response, the primary and secondary analyses will not adjust for these other characteristics because the modest sample size makes such adjustments impractical. The randomization procedure will be relied upon to avoid favoring either treatment arm in the safety and efficacy comparisons. Exploratory analyses may be conducted to attempt to adjust for one or more additional variables.

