3.3 Treatment Masking (Blinding)

This is an unblinded trial, but the person interacting with the imaging software is to be blinded to treatment arm to avoid bias between arms for purposes of measuring the secondary outcome. This is because wound area calculations used by the software rely on an individual manually outlining the wound within the imaging software.

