3.4 Study Intervention Compliance

As part of the work-flow for assessments at Visits 2–5, the subject will be asked if any investigational wound care has been received since the last study visit that is external to that described in the protocol. Subjects who received investigational wound care between Visits 1 and 2 are not to be randomized as the protocol does not allow such individuals to receive any pAF injections during the study. Subjects randomized to the pAF arm who receive external wound care between Visits 2 and 3 are not eligible to receive pAF at Visit 3. Follow-up data at Visits 2–5 should still be collected on all individuals who were randomized to a treatment arm at Visit 2, regardless of study intervention compliance. The only exceptions to the desire to follow-up are for individuals who die or formally withdraw during the study.

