5.2 Methods for Withdrawals, Missing Data, and Outliers

The applicability of some measures will depend on whether or not the wound is (or has previously) closed. Values that are not observed because they are not applicable will be excluded from the pertinent analyses, rather than regarded as missing. Values that are not directly obtained but are implied by other measurements will use the implied value.

Multiple imputation (MI) will be applied for analyses of the secondary outcome. Using MI leverages partial information and attempts to reduce bias in final inferences that could result from a naive complete-case analysis. A minimum of ten data sets will be generated. Chained equations will be used along with variable selection; for imputing missing values for a given variable, the input variables will be limited to those that increase the R^2 value by at least 0.01. If feasible, MI will be conducted separately within each treatment arm. The pool of variables for the imputation process includes: wound area per the imaging software at Visits 1, 2, 3, 4, and 5; treatment arm if infeasible to impute by treatment arm; and indicators for comorbidities. The following comorbidities will be considered: diabetes, peripheral vascular disease, and immunosuppression. Imputation will exclude individuals

who were not randomized.

Visit measurements obtained outside the permissible window may or may not be used in the imputation model. We will determine the closest visit number to assign the out-of-window visit per the protocol's timing for follow-up visits. The out-of-window measurement will be used for the determined visit number in the case that the visit number does not already have a valid measurement (and if there are multiple out-of-window candidate measurements, the one closest to the protocol timing will be used). Otherwise, the out-of-window measurement will be ignored.

Multiple imputation may also be used for exploratory outcomes, as appropriate.

We do not plan to use different methods for missing data due to withdrawal compared with data missing for other reasons.

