7.4 Exploratory Outcome(s) Analyses

7.4.1 Wound Area Reduction at Visits 3, 4

The percent reduction in wound area at Visit 3 (4) relative to Visit 2 will be summarized overall and by assigned treatment arm for the ITT population. If there are study visits outside of the visit's ± 1 week window, all percentages will be divided by the number of elapsed days since visit 2, so the outcome is expressed as a percentage change per day. The summary will include means and standard deviations or medians and interquartile ranges, as appropriate.

If the change in wound size at Visit 3 (4) follows a reasonably symmetric distribution within each treatment arm, then a two-sided, two-sample, unpooled t-test will be performed to compare the mean reductions at Visit 3 (4) between arms for the ITT population. If the distribution is very asymmetrical in one or both arms, a Wilcoxon rank sum test will be used.

7.4.2 Wound Area Reduction at Visits 3, 4, 5, per rectangular wound area approximation

The secondary outcome relies on wound images that are compatible for use with the imaging software. However, there is also interest in assessing reduction in wound area for wound areas calculated with the rectangular approximation. The area per rectangular approximation at visit k , $RectangularApprox_k$, is defined as:

$$RectangularApprox_k \equiv MaxWidth_k \times MaxLength_k,$$

where $MaxWidth_k$ and $MaxLength_k$ are the maximal width and length (in cm), at Visit k , respectively.

As an exploratory outcome, the percent reductions per rectangular approximation at Visits 3, 4, and 5 relative to Visit 2 will be analyzed in the same manner as for the percent reductions per imaging software. Each analysis of the rectangular wound area approximations is considered an exploratory analysis to gauge the sensitivity of the secondary outcome analysis.

7.4.3 Wound Closure at Visit 5

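### The two missing-data sensitivity runs for wound area move both arms in the same direction, so with similar missingness neither tests missing pAF outcomes being worse and missing SOC outcomes better than imputed

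*SAP*

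**What the plan says.** The main analysis of the secondary outcome is multiple imputation from software wound areas at all visits and three comorbidities. SAP 5.2 adds: "If feasible, MI will be conducted separately within each treatment arm". Withdrawals are handled like other missing data.

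SAP 7.3.1 then plans the robustness check: "Two sensitivity analyses will be conducted in which missing values are replaced with the lowest (highest) observed value in the assigned treatment arm". Protocol section 8 (Statistical Method) agrees, "first replacing each missing outcome with the lowest observed outcome at that timepoint from among subjects in the same assigned treatment arm", followed by a second run with the highest value. Neither document plans a delta-adjusted, tipping-point or opposite-direction run.

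Four other provisions bear on the point.
- **Follow-up after stopping pAF.** The protocol says "we will continue to follow the patient and monitor for safety and efficacy endpoints" (Discontinuation of Study Drug). SAP 3.4 says "The only exceptions to the desire to follow-up are for individuals who die or formally withdraw during the study".
- **How an area can still be missing.** The note to protocol Table 3 says "Applicable study procedures may be completed via telehealth or by phone, at the discretion of the treating provider". SAP 7.4.2 says "The secondary outcome relies on wound images that are compatible for use with the imaging software".
- **What reduces the missingness.** SAP 5.2 uses a value implied by other measurements where the direct one is absent, and SAP 7.4.4 equates closure with zero area. SAP 7.4.2 repeats the analysis on length times width, which is measured manually at every visit.
- **Blinding.** SAP 3.3: "This is an unblinded trial". Only the person outlining the image is masked.

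**The concern.** A missing-data sensitivity analysis should show how far the between-arm comparison depends on the assumption behind the imputation. The harmful departure is one that differs by arm. Patients and staff know the assignment, so reasons for a missing Visit 5 area could differ between pAF and SOC. If missing pAF wounds did worse than imputed and missing SOC wounds did better, the imputed difference would favour pAF too much. Filling both arms low, then both high, changes the level of both arms but hardly changes their difference when the arms have similar missing counts. The two runs could then agree with each other and with a spurious main result, and that agreement would be read as robustness.

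**Working it through.** **Inputs.** SAP 8 gives 30 per arm, closure (100% reduction) with probability 0.5 for pAF and 0.2 for SOC, and otherwise a uniform reduction from 0 to 100%. It assumes all 60 outcomes are observed. No missing rate is given, so 3/30 and 6/30 per arm are assumed.

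**The plan's own figure.** Simulating the SAP 8 scenario (20,000 trials, two-sided Wilcoxon) gives 53.8% power, or 53.5% with continuity correction, against the stated 54%. Arm means are 0.5×100 + 0.5×50 = 75 and 0.2×100 + 0.8×50 = 60, a difference of 15.

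**Step 1: the planned runs.** With a share f missing at random in each arm and fills c_pAF and c_SOC, the mean difference is 15(1−f) + f(c_pAF − c_SOC). Average observed minima from simulation are 7.2 (pAF) and 4.5 (SOC) at 3/30, and 8.0 and 5.0 at 6/30. The maximum is in effect 100 in both arms.

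| Fill | 3/30 per arm | 6/30 per arm |
|---|---|---|
| Both low (planned) | 13.5 + 0.1×(7.2−4.5) = 13.8 | 12.0 + 0.2×(8.0−5.0) = 12.6 |
| Both high (planned) | 13.5 + 0 = 13.5 | 12.0 + 0 = 12.0 |
| pAF low, SOC high | 13.5 + 0.1×(7.2−100) = 4.2 | 12.0 + 0.2×(8.0−100) = −6.4 |
| pAF high, SOC low | 13.5 + 0.1×(100−4.5) = 23.1 | 12.0 + 0.2×(100−5.0) = 31.0 |

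Direct simulation agrees. The planned pair spans less than a point; the opposed pair, which is not planned, spans 19 to 37 points.

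**Step 2: where cancelling fails.**
- With 6/30 missing in pAF and 3/30 in SOC, the planned runs give 7.1 and 16.0.
- With 6/30 missing in pAF only, they give 1.6 and 20.0, and an opposed run would add nothing.
- If open wounds could reach −50% in pAF only, 3/30 per arm gives −2.1 and 2.2 against 2.5 observed.

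**Step 3: false reassurance with no true effect.** Assumptions: 20% closure in both arms; 6/30 missing per arm, drawn from the lower 15 outcomes in pAF and the upper 15 in SOC; ten by-arm imputations from Visit 4 only; Visit 4 to Visit 5 correlation 0.5 or 0.7; mean difference with Rubin's rules; fills tested by unpooled t-test; significance counted in favour of pAF.

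| | Closed wounds can be missing | Closure known |
|---|---|---|
| Imputation falsely significant | about 14–22% | about 9–14% |
| Of those, both planned runs stay significant | about 64–80% | about 44–59% |

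An opposite 20-point shift (pAF down, SOC up) leaves only about 20–24% of those falsely significant trials significant. When closed wounds can be missing, imputation averages a false benefit of 11.1 points (correlation 0.5) or 8.3 (0.7), and the planned fills show about 11.5 and 11.1. When closure is known, the planned runs separate, to about 4 and 11 points. Repeat simulations differ by about five points (69–84% in place of 64–80%), so these percentages are approximate.

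**Step 4: a delta shift when the effect is real.** SAP 8 scenario, missing at random, correlation 0.7. Before the cap at 100%, an opposite 20-point shift moves the difference by 2×20×0.1 = 4 points at 3/30 and 2×20×0.2 = 8 at 6/30. In simulation, with the cap, the imputed difference falls from 14.8 to 11.2 and from 14.7 to 7.5, and significance is lost in 37% and 64% of significant trials. Shifting both arms 20 points the same way leaves 14.8 or 14.5 (3/30) and 14.7 or 14.1 (6/30), and loses significance in at most 7%.

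**The case against.** **Some missing areas are recoverable.** A wound recorded as closed at a remote visit arguably has an implied area of zero under SAP 5.2. An in-person visit with an unusable image still yields length and width for SAP 7.4.2. SAP 5.2 also admits some out-of-window measurements. This stands, and it narrows the gap to withdrawals, missed visits and remote visits without a measurement. It does not close it.

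**The planned runs are not empty.** They move with unequal missingness. In the SAP 8 scenario with a means-based test, the low and high fills lose significance in 30% and 15% of significant trials at 3/30, and in 45% and 27% at 6/30. With a Wilcoxon test on complete cases in the Step 3 loss pattern, at least one fill lost significance in 46% (3/30) and 60% (6/30) of falsely significant trials. This also stands. With equal missingness, though, the loss comes from added ties and spread, not from testing an arm-specific departure.

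**The simulation is a simplification.** The plan imputes from more variables, and SAP 8 expects a Wilcoxon test. The loss pattern in Step 3 is extreme. The percentages illustrate a mechanism and do not forecast this trial.

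**Stronger readings that the documents do not support.** A reader might infer that stopping pAF creates missing outcomes, but both documents continue follow-up except after death or formal withdrawal. A reader might also take the two runs as claimed bounds, but the documents call them only sensitivity analyses.

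**Conclusion.** The point holds in a limited form. With similar missingness and similar extremes in the two arms, the planned low and high runs change the mean difference by about 1 to 3 points from 15. No planned analysis covers missing pAF outcomes being worse, and missing SOC outcomes better, than imputed. With unequal missingness the runs are informative, and with missing data in one arm only nothing is left out.

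The size rests on assumed missing rates, loss patterns and correlations, since the documents give none. It would be wrong to infer that the secondary result is biased or that the trial's decision is at risk: nothing shows that informative loss will occur, SAP 8 puts power at about 54%, and the decision to proceed rests on related SAEs in the pAF arm. What is affected is how robust the efficacy result appears. This is a cheap improvement.

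**What to change.** In SAP 7.3.1 and protocol section 8, keep the two planned runs and add an arm-specific delta-adjusted analysis on the existing imputations.
- **Directions and grid.** pAF shifted down with SOC shifted up, and the reverse, over a short grid such as 0, 10, 20 and 30 points.
- **Scale.** Shift the imputed Visit 5 percent reduction, capped at 100%, before any per-day conversion under SAP 7.3.
- **Statistic.** Mean difference with Rubin's rules.
- **Reporting.** State the shift at which the conclusion changes, as description and not as a pass/fail test.
- **Timing.** Fix the grid in a dated SAP amendment before arm-level efficacy results are produced. The DCC biostatisticians attend closed sessions that use actual assignments (SAP 6.4).

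Opposed extreme fills are best left out, or reported only as descriptive extremes: the adverse one removes significance in 88% (3/30) and 99% (6/30) of significant trials even when the effect is real.

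**Cost.** Wording in two documents and no new data. Equal shifts in both arms need 3 + 3 + 1 = 7 scenarios; varying the arms independently needs 16 + 16 − 1 = 31. Each runs on at least ten imputed data sets, dual-programmed if in the primary report (SAP 5.6). A true effect may look less robust (Step 4), so the team should judge in advance which shifts are plausible.

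**Separate item, not counted here.** Protocol section 8 applies the lowest/highest rule to the primary outcome too, while SAP 7.2.1 counts every randomized subject without follow-up through Visit 5 as having an event. The two should be reconciled. With no events in 30, the protocol rule cannot change the 90% bound; the SAP rule gives 76%, 68% or 64% with 3, 5 or 6 incomplete.

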7.4 Exploratory Outcome(s) Analyses

7.4.1 Wound Area Reduction at Visits 3, 4

The percent reduction in wound area at Visit 3 (4) relative to Visit 2 will be summarized overall and by assigned treatment arm for the ITT population. If there are study visits outside of the visit's ± 1 week window, all percentages will be divided by the number of elapsed days since visit 2, so the outcome is expressed as a percentage change per day. The summary will include means and standard deviations or medians and interquartile ranges, as appropriate.

If the change in wound size at Visit 3 (4) follows a reasonably symmetric distribution within each treatment arm, then a two-sided, two-sample, unpooled t-test will be performed to compare the mean reductions at Visit 3 (4) between arms for the ITT population. If the distribution is very asymmetrical in one or both arms, a Wilcoxon rank sum test will be used.

7.4.2 Wound Area Reduction at Visits 3, 4, 5, per rectangular wound area approximation

The secondary outcome relies on wound images that are compatible for use with the imaging software. However, there is also interest in assessing reduction in wound area for wound areas calculated with the rectangular approximation. The area per rectangular approximation at visit k , $RectangularApprox_k$, is defined as:

$$RectangularApprox_k \equiv MaxWidth_k \times MaxLength_k,$$

where $MaxWidth_k$ and $MaxLength_k$ are the maximal width and length (in cm), at Visit k , respectively.

As an exploratory outcome, the percent reductions per rectangular approximation at Visits 3, 4, and 5 relative to Visit 2 will be analyzed in the same manner as for the percent reductions per imaging software. Each analysis of the rectangular wound area approximations is considered an exploratory analysis to gauge the sensitivity of the secondary outcome analysis.

7.4.3 Wound Closure at Visit 5

An exploratory endpoint is whether or not the randomized wound is closed at Visit 5. Fisher's exact test will be used to test for an association between treatment arm and whether the wound is closed at Visit 5. This will be assessed for the ITT population. In the principal analysis of this outcome, only participants with a nonmissing Visit 5 wound closure status will be included. If feasible, multiple imputation will be used to fill in missing wound closure statuses, with candidate variables in the imputation model possibly including variables such as treatment arm, wound closure status at visits 3 and 4, wound area at Visit 1 per the imaging software, and percent reduction in wound area from Visit 1 to Visit 2.

7.4.4 Wound Closure Prior to Visit 5

Another exploratory endpoint is whether or not the randomized wound was closed at Visit 3 and/or Visit 4, regardless of whether it later recurred. This will be determined by having the wound area per the imaging software assessment be equal to 0. The number and percentage of wounds closed prior to Visit 5 will be summarized, overall and by treatment arm, for the ITT population.

7.4.5 Wound Recurrence at Visit 5

This exploratory endpoint is limited to those from the ITT population whose randomized wound closed prior to Visit 5. Among this subset, the number and percent whose wound was open at the time of Visit 5 will be reported overall and by treatment arm. If the denominator is not zero, the corresponding percentage will also be displayed, overall and by treatment arm.

7.4.6 Hypertrophic Scar Formation at Visit 5

This exploratory endpoint is measured by the modified Vancouver Scar Scale (mVSS) total score and is applicable to those from the ITT population whose randomized wound is closed at Visit 5. Among this subset, the mean and standard deviation (or median and interquartile range) will be summarized overall and by treatment arm for the applicable subjects with nonmissing mVSS total scores.

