3.2 Method of Treatment Assignment and Randomization

Subjects will be randomized into two groups at a 1:1 ratio. The randomization will employ random block sizes of two, four, or six subjects to limit the ability to predict the next subject's treatment prior to randomization. It is not guaranteed that exactly 30 subjects will be randomized to each arm due to random block sizes and the unlikely event of administering backup randomization for a subject. There may be as few as 28 in the pAF arm (32 in the standard of care–SOC–arm) or as many as 32 in the pAF arm (28 in the SOC arm). Because of the small number of overall patients and the anticipated slow accrual rate, stratification by subject characteristics will not be used in the randomization procedure.

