5 GENERAL ISSUES FOR STATISTICAL ANALYSES

5.1 Analysis Software

Analysis will be performed using SAS® Software version 9.4 or later whenever possible. Other software packages, including R and StatXact®, may be used for particular specialized procedures. IVEware is the preferred software for creating the study's multiply imputed data sets.

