5.3 Multiple Comparisons and Multiplicity

There is one primary endpoint (occurrence of post-randomization study-related SAEs on or before Visit 5), which is not intended to be tested between arms. Instead, descriptive summaries and confidence intervals will be constructed by study arm. There is one secondary endpoint (percent reduction in wound area at Visit 5 compared to Visit 2), which will be tested at $\alpha = 0.05$. The additional analyses are regarded as exploratory and therefore no adjustments are indicated for the multiplicity of testing; each will use $\alpha = 0.05$.

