8 SAMPLE SIZE DETERMINATION

A sample size of $n = 30$ patients per group (total $n = 60$) is expected, though this may differ slightly because of the randomization procedure. Thirty participants in the pAF group with no study-related serious adverse events will provide a lower bound of the 95% one-sided exact binomial confidence interval for safety of 90% and provide enough evidence to move on to the next phase of study.

The power calculation depends on several assumptions:

- That 30 subjects are assigned to each treatment arm and that the secondary outcome is observed for all 60 subjects;
- That each subject has wound closure at Visit 5 (i.e., 100% wound area reduction relative to Visit 2) with probability $p_{SOC} = 0.2$ or $p_{pAF} = 0.5$ in the SOC and pAF arms, respectively; AND
- That for the remaining subjects in each arm, the wound area reduction percentage is uniformly distributed between 0% and 100%.

Using the Wilcoxon rank sum test (in this scenario, the response is very skewed in the pAF treatment arm), the Monte Carlo estimate of power is approximately 54%.

The trial has only modest power to detect statistically significant efficacy of pAF, but this is not unexpected for a phase I/II trial. More importantly, the sample size is sufficiently large to support the safety of moving on to the next phase of study if no study-related SAEs occur in the pAF arm, and the next phase of study would be appropriately powered for assessing efficacy.

pAF_in_Wounds_SAP_v_1_0

Final Audit Report

2021-03-11

Created: 2021-03-11
By: [name] ([contact])
Status: Signed
Transaction ID: CBJCHBCAABAAvUMP3dZCaNupqQJtavUadHtUrEKt9kc0

"pAF_in_Wounds_SAP_v_1_0" History

-  Document created by [name] ([contact])
2021-03-11 - 10:42:19 PM GMT- IP address: [name]
-  Document emailed to [name] MD ([contact]) for signature
2021-03-11 - 10:43:29 PM GMT
-  Email viewed by [name] MD ([contact])
2021-03-11 - 11:51:14 PM GMT- IP address: [name]
-  Document e-signed by [name] MD ([contact])
Signature Date: 2021-03-11 - 11:51:42 PM GMT - Time Source: server- IP address: [name]
-  Agreement completed.
2021-03-11 - 11:51:42 PM GMT

Adobe Sign

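### Wound closure at Visit 5 (exploratory): Fisher's exact test is valid but conservative, and Boschloo's exact test would be more powerful in most settings and never less powerful, within the same 5% limit

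*SAP*

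**What the plan says.** SAP 7.4.3 gives the status of the endpoint: "An exploratory endpoint is whether or not the randomized wound is closed at Visit 5". It then states that Fisher's "exact test will be used to test for an association between treatment arm and whether the wound is closed at Visit 5". Protocol section 8 (Statistical Considerations) prescribes the same test. Neither document says whether the test is one- or two-sided, gives a reason for choosing Fisher, or asks for an effect estimate or interval. SAP 5.3 sets alpha at 0.05 for each exploratory analysis, without adjustment for multiplicity.

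The principal closure analysis uses only patients whose Visit 5 closure status is known. SAP 3.2 allows final allocation to range from 28:32 to 32:28.

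The documents state no power for the closure test. SAP 8 does supply closure rates, as part of the power scenario for the secondary outcome: closure "with probability $p_{SOC} = 0.2$ or $p_{pAF} = 0.5$ in the SOC and pAF arms, respectively", under the assumption "That 30 subjects are assigned to each treatment arm and that the secondary outcome is observed for all 60 subjects". SAP 5.1 says that R and StatXact, among other packages, "may be used for particular specialized procedures".

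**The concern.** Fisher's test conditions on the total number of closed wounds, which this design does not fix in advance. In a trial of this size the conditional distribution has few possible values, so the test usually cannot come near 5% and its actual error rate stays well below the nominal level. Part of the allowed error rate goes unused, and power is lost with it.

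Boschloo's test takes Fisher's p-value as its statistic and finds the largest probability, over all common closure rates, of a value at least as small. Fisher's test never exceeds its nominal level, so that probability is never larger than Fisher's own p-value. Every table that Fisher rejects is therefore also rejected by Boschloo, which still holds the 5% limit.

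What is at stake is the sensitivity of one exploratory comparison. It is a clinically plain one, and its results are likely to be read when the next phase is planned.

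**Working it through.** **1. The plan's own figure.** SAP 8 gives about 54% power for the Wilcoxon test on percent area reduction, with 30 per arm, closure 20% versus 50%, and open wounds uniform between 0 and 100%. A simulation of 40,000 trials gives 54.2% without continuity correction and 53.8% with it. The stated figure reproduces. It belongs to the secondary outcome, not to the closure test.

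**2. Inputs for the closure test.** Arms of 30 and closure rates of 0.20 (SOC) and 0.50 (pAF) come from SAP 8, and alpha 0.05 from SAP 5.3. A two-sided test is my assumption.

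**3. Method.** All 31 × 31 = 961 possible tables were enumerated. With a closed wounds on SOC, b on pAF, and R the set of tables that a test rejects:

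- Power = sum over (a, b) in R of Bin(a; 30, 0.20) × Bin(b; 30, 0.50).
- Maximum size = the largest value, over a common rate p, of the sum over R of Bin(a; 30, p) × Bin(b; 30, p), on a grid of 2,000 values from 0.0005 to 0.9995.

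**4. Results at 30:30.**

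| Test | Maximum size | Power, 20% v 50% |
|---|---|---|
| Fisher | 2.74% | 59.6% |
| Boschloo | 4.69% | 67.1% |
| Pearson chi-square, uncorrected | 5.5% | 69.2% |

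Fisher's actual size is 0.94% at a common closure rate of 0.1, 2.2% at 0.2, 2.6% at 0.35 and 2.7% at 0.5. Boschloo rejects 32 tables that Fisher does not, and the reverse never happens. For example, 15/30 versus 7/30 closed gives p = 0.060 by Fisher and p = 0.035 by Boschloo. Fisher would need 34 per arm to reach at least 67.1% power (65.7% at 33), which is 2 × (34 − 30) = 8 more patients. The uncorrected chi-square exceeds 5% and is not a suitable substitute.

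**5. Sensitivity to the analysed arm sizes (20% v 50%).** Gains are taken before rounding.

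| pAF : SOC | Fisher size | Fisher power | Boschloo size | Boschloo power | Gain, points |
|---|---|---|---|---|---|
| 30:30 | 2.7% | 59.6% | 4.7% | 67.1% | 7.4 |
| 29:29 | 2.5% | 57.2% | 4.8% | 67.1% | 9.9 |
| 27:27 | 2.6% | 55.0% | 4.5% | 62.7% | 7.7 |
| 25:25 | 3.3% | 51.0% | 4.6% | 60.6% | 9.6 |
| 31:29 | 3.9% | 65.1% | 4.7% | 69.2% | 4.1 |
| 29:31 | 3.9% | 62.2% | 4.7% | 68.6% | 6.4 |
| 30:29 | 3.6% | 62.2% | 4.7% | 67.0% | 4.8 |
| 28:32 | 3.7% | 64.3% | 5.0% | 70.4% | 6.2 |
| 28:27 | 3.8% | 60.1% | 4.7% | 63.4% | 3.3 |

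The 5.0% at 28:32 is 4.96% before rounding.

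If blocks of 2, 4 and 6 are equally likely (an assumption; SAP 3.2 gives the sizes but not their probabilities), about 81% of simulated randomizations of 60 patients end at exactly 30:30. Missing Visit 5 closure status can still make the analysed arms unequal.

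**6. Sensitivity to the closure rates.** At 30:30, 25% versus 50% gives 41.3% for Fisher and 50.2% for Boschloo, and the gain for 20% versus 40% is about 5 points. With 28 on pAF and 32 on SOC, the gain is under 0.5 points for 10% versus 30% and practically nil for 5% versus 20%. No setting computed gave a loss.

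**The case against.** Fisher's test keeps the 5% level, so the plan contains no error here. The choice between conditional and unconditional exact tests is a long-standing matter of preference. Under a strict randomization argument with no effect on any patient, the total number of closures is in fact fixed. Closure is also one of many exploratory tests run unadjusted at 0.05, so a conservative test can be defended. Progression to the next phase rests on safety (SAP 8), and no decision depends on this p-value.

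Most of this stands, and it is why the priority is low. It does not justify keeping Fisher. Once alpha is set at 0.05, a test that respects that limit and is never less powerful is the better choice. If stricter control is wanted, a smaller stated alpha is a clearer way to get it than an unstated loss that changes with arm size.

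Three stronger readings are tempting, and the documents do not support them:

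- A reader might infer that the true error rate is below 3% and the loss about 7 points in this trial generally. The combination describes 30:30. The unequal arms made possible by SAP 3.2 and the complete-case rule give 3.6 to 3.9% and about 3 to 6 points.
- A reader might infer that the change helps with the modest power conceded in SAP 8. That remark and the 54% concern the Wilcoxon test on area reduction. The 20% and 50% closure rates enter there only as the share of patients with 100% reduction.
- A reader might infer that the change is free. Fisher's test is also written into the protocol, and Protocol section 10 (Amendments) requires IRB review and approval of any change. The actual false-positive rate also rises, although it stays within 5%.

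**Conclusion.** The point holds as a low-priority gain in efficiency on an exploratory endpoint. At SAP 8's planning inputs with a two-sided test, Boschloo's test raises power from 59.6% to 67.1% and the maximum type I error from 2.7% to 4.7%. With slightly unequal arms the gain at 20% versus 50% is about 3 to 6 points. At other closure rates it may be larger, smaller or practically zero. That it cannot be negative follows from the construction of the test and does not depend on the assumed rates. The sizes quoted do depend on those rates, on the analysed arm sizes and on two-sided testing.

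**What to change.** In SAP 7.4.3 and Protocol section 8, before any closure results are compared by arm, replace Fisher's exact test with the two-sided Boschloo exact unconditional test at 0.05 for the principal complete-case analysis. Name this one test and leave no alternative open. Barnard's test with the pooled z statistic is slightly more powerful at 30:30 (67.8%), but at 28 pAF and 32 SOC it is less powerful than Boschloo (67.6% against 70.4%).

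Add the closure-rate difference, pAF minus SOC, with an exact unconditional 95% confidence interval, and state which statistic is inverted to obtain it. If that statistic differs from the one behind the p-value, the two can disagree in borderline tables, so the SAP should say which governs.

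The optional multiple-imputation analysis of closure lies outside this change. SAP 7.4.3 gives no rule for combining an exact test across imputed data sets, and the change does not supply one.

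The cost is a SAP edit, a minor protocol amendment with IRB review, and a higher actual false-positive rate that stays at or below 5%. No extra patients, visits or data are needed, and SAP 5.1 already permits suitable software.
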